7.5. Height, Weight, and Physical Examination

Standing height (in cm) will be measured at Screening/Baseline on Visit 1, Week 12 (Visit 2), Week 24 (Visit 3), Week 36 (Visit 4), Week 48 (Visit 5), Week 60 (Visit 6), Week 72 (Visit 7), Week 84 (Visit 8), Week 96 (Visit 9) Week 108 (Visit 10), Week 120 (Visit 11), Week 132 (Visit 12), Week 144 (Visit 13- End-of-Treatment/Premature Discontinuation), and at the Post-Treatment visit (6 weeks post discontinuation of study drug).

For nonambulatory patients, due to the difficulty in obtaining an accurate standing height measurement, ulna length and arm span will be used as a surrogate measure for height (see Study Manual). Ulna length and arm span (in cm) will be measured at Screening/Baseline on Visit 1, Week 12 (Visit 2), Week 24 (Visit 3), Week 36 (Visit 4), Week 48 (Visit 5), Week 60 (Visit 6), Week 72 (Visit 7), Week 84 (Visit 8), Week 96 (Visit 9) Week 108 (Visit 10), Week 120 (Visit

11), Week 132 (Visit 12), Week 144 (Visit 13 - End-of-Treatment/Premature Discontinuation), and at the Post-Treatment visit (6 weeks post discontinuation of study drug).

Weight (in kg) will be measured at Screening/Baseline on Visit 1, Week 12 (Visit 2), Week 24 (Visit 3), Week 36 (Visit 4), Week 48 (Visit 5), Week 60 (Visit 6), Week 72 (Visit 7), Week 84 (Visit 8), Week 96 (Visit 9) Week 108 (Visit 10), Week 120 (Visit 11), Week 132 (Visit 12), Week 144 (Visit 13- End-of-Treatment/Premature Discontinuation), and at the Post-Treatment visit (6 weeks post discontinuation of study drug).

A full physical examination (including evaluation of cardiovascular system, chest and lungs, thyroid, abdomen, nervous system, skin and mucosae, musculoskeletal system, eyes, ears, nose, mouth, throat, spine, lymph nodes, extremities, and genitourinary) will be conducted at Screening/Baseline (Visit 1), Week 48 (Visit 5), and Week 96 (Visit 9) and Week 144 (Visit 13 – End of Treatment/Premature Discontinuation) visit.

Physical exams may also be performed at any time during the study as clinically indicated.

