10.4.3. Primary Variables – Safety

Vital signs (height, weight, systolic and diastolic blood pressure, radial pulse rate, and body temperature) and physical examination data will be listed and summarized by visit and overall. Where appropriate, changes from baseline at each visit will be summarized and tested by means of the paired t-test or a nonparametric alternative.

Adverse events will be classified using the MedDRA classification system. The severity of adverse events will be graded according to the CTCAE, Version 3.0, whenever possible.

The frequency of patients experiencing a specific adverse event will be tabulated by treatment period and for the whole study, categorizing events by body system, and MedDRA term. In the by-patient analysis, a patient having the same event more than once will be counted only once. Adverse events will be summarized by worst CTCAE grade within a patient.

Adverse events classified as CTCAE Grade 3 or higher; study-drug-related events; adrenal, hepatic, and renal events leading to special diagnostic evaluations; events leading to discontinuation from treatment; and SAEs will be considered with special attention.

No attempt will be made to reconcile data collected from the patient/caregiver-reported outcome instruments with adverse event reporting.

Hematological data will be summarized by treatment period and overall. Hematological data will be graded according to CTCAE severity grade. The frequencies of the worst severity grade observed will be displayed by worst CTCAE grade within a patient.

Serum biochemistry and urine data (including parameters for assessment of adrenal, hepatic, and renal monitoring – see [Section 6.3.1](#)) will be summarized by treatment period and overall. Values will be graded according to CTCAE severity grade, when applicable. For variables graded according to CTCAE severity grade, the frequencies of the worst severity grade observed will be displayed within a patient. For parameters for which a CTCAE scale does not exist, the frequency of patients with values below, within, and above the normal ranges will be summarized.

Urinalysis data will be listed and summarized by treatment period and overall, and will be checked for changes from baseline over time.

The results of an ultrasound to examine the kidneys and collecting system will be listed and abnormal results will be noted and investigated in terms of their relation to other relevant patient outcome measurement.

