13.2.7. Blood Pressure Assessment

During the Phase 2b double-blind study of ataluren in nmDMD (PTC124-GD-007-DMD), 6 patients – all receiving corticosteroids – had hypertension (or increased blood pressure) reported as adverse events (0 for ataluren 20, 20, 40 mg/kg, 5 for ataluren 10, 10, 20 mg/kg, and 1 for placebo). For this reason, blood pressure will be monitored via standardized procedures at each visit.

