#### **Safety**

- Change from baseline in other safety parameters (eg, vital signs)

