### **5.7.2. Laboratory Tests**

Hematological, serum biochemistry, adrenal laboratories, and urine data and their changes (only for continuous laboratory parameters) from baseline will be summarized by visit.

Shift tables for hematology and biochemistry data will also be presented showing change in CTCAE severity grade from baseline to each visit. For parameters for which a CTCAE scale does not exist, shift tables will be presented showing change in results from baseline (normal, low and high [or abnormal]) to each visit (normal, low and high [or abnormal]).

Summary of abnormalities in laboratory variables pre-defined for safety monitoring will be done per the following Table 2.

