## 5.8. Other Variables

### 5.8.1. Vital Signs

Vital signs (systolic and diastolic blood pressure, pulse rate, body weight, height, ulna length, arm span, and body temperature) will be summarized by visit for overall subjects.

Number (%) of subjects with meeting hypertension criteria as the following will be summarized.

- If age <18 years old, the hypertension criteria are based on age, gender, and height-adjusted systolic blood pressure (SBP) and diastolic blood pressure (DBP) percentile results (Hypertensive:  $\geq$  95th percentile; Pre-hypertensive: 90 - < 95th percentile; Normal: < 90th percentile).
- If age  $\geq$  18 years old, hypertensive: SBP  $\geq$  140 mmHg or DBP  $\geq$  90 mmHg; pre-hypertensive: SBP 120 - 139 mmHg or DBP 80 - 89 mmHg; Normal: SBP 90 - 119 mmHg and DBP 60 - 79 mmHg.

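### SAP 5.8.1 leaves out the change-from-baseline summary for vital signs without declaring it, and its hypertension count has no visit or baseline status

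*SAP*

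**What the plan says.** Both documents list the same secondary safety endpoint in section 3.3: "Change from baseline in other safety parameters (eg, vital signs" (the closing bracket follows).

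For vital signs, protocol 10.4.3 states: "Where appropriate, changes from baseline at each visit will be summarized and tested by means of the paired t-test or a nonparametric alternative". SAP 5.8.1 has two elements. The first is a summary of values: "ulna length, arm span, and body temperature) will be summarized by visit for overall subjects". The second is a count: "Number (%) of subjects with meeting hypertension criteria as the following will be summarized". For patients under 18 the criteria are age-, sex- and height-adjusted percentiles, with hypertensive set at the 95th or above. For adults they are fixed cut-offs.

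SAP 7 lists the departures from the protocol: the supportive 6-minute walk analyses and all paired t-tests are removed. Nothing is said about the descriptive vital-sign changes. SAP 1 makes the SAP prevail where the two documents conflict.

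Protocol 13.2.7 describes the hypertension reports in Study 007 and concludes: "For this reason, blood pressure will be monitored via standardized procedures at each visit".

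**The concern.** A named endpoint has no analysis assigned to it, and the list of declared changes does not mention this. Dropping a paired t-test does not drop the mean change that it would have tested.

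The hypertension count does not fill the gap. A patient who was hypertensive at entry and stayed so counts the same as one who became hypertensive during the study. All six Study 007 patients with such reports were on corticosteroids, so some pre-existing elevation in a similar population is plausible. Long-term safety is the primary objective of this extension, and blood pressure is one of the few parameters to which the protocol gives its own monitoring rationale.

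**Working it through.** **1. Is the change specified anywhere?** The plan has no figure to reproduce here, so the check is textual.

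- The laboratory section names it: "urine data and their changes (only for continuous laboratory parameters) from baseline will be summarized by visit".
- SAP 5.8.3 to 5.8.9 (walk test, timed tests, NSAA, PODCI, spirometry, upper limb, daily-living survey) each name change from baseline. SAP 5.8.10 (renal ultrasound) names a shift table.
- SAP 5.8.1 names neither. SAP 6.3 gives a general formula for change but assigns it to no variable.

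The accurate statement is that the SAP never specifies the change for vital signs.

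**2. What can the hypertension count show?** Take N = 220 (the upper bound in SAP 3.4). Assume that 30% meet the criteria, which is 66 patients, including everyone hypertensive at baseline. With baseline prevalence b, new cases = 66 − 220b, and the rate among those at risk = new cases / (220 − 220b).

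| b (assumed) | Hypertensive at baseline | New cases | Rate among those at risk | Planned count |
|---|---|---|---|---|
| 0% | 0 | 66 | 66/220 = 30.0% | 66 |
| 10% | 22 | 44 | 44/198 = 22.2% | 66 |
| 20% | 44 | 22 | 22/176 = 12.5% | 66 |
| 30% | 66 | 0 | 0/154 = 0% | 66 |

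The planned table is identical in all four rows.

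**3. How strong is the prior signal?** The counts are from protocol 13.2.7 and the arm sizes from protocol 2.2.3. Intervals are exact (Clopper-Pearson).

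- 10, 10, 20 mg/kg: 5/57 = 8.8% (95% CI 2.9 to 19.3)
- Placebo: 1/57 = 1.8% (0.04 to 9.4)
- 20, 20, 40 mg/kg: 0/60 = 0% (0 to 6.0)

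Fisher's exact test of 5/57 against 1/57 gives two-sided p = 0.21.

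**4. Would a worst-value shift table be enough?** There are 12 post-baseline treatment visits (Weeks 12 to 144). Suppose one blood-pressure measure has a 5% chance per visit of reaching the 95th percentile, with no drug effect. With independent visits, the chance of at least one such reading is 1 − 0.95^12 = 46%.

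For correlated visits I simulated a normal model with equal correlation between visits (400,000 draws, threshold z = 1.645), keeping only patients below the threshold at baseline. All correlations are assumptions.

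| Within-patient correlation | At least one visit | Two consecutive visits |
|---|---|---|
| 0 | 46% | 3% |
| 0.5 | 24% | 5% |
| 0.8 | 12% | 4% |

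A worst-value shift therefore needs the consecutive-visit count beside it.

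**5. What else would catch a new elevation?** Protocol 8.1.1 requires a test abnormality to be reported as an adverse event only when it needs intervention or investigation beyond a repeat test. Appendix A prompts action for hypertension at the 99th percentile lasting at least 6 weeks, whereas the SAP criterion is the 95th. An elevation between the two need not become an adverse event.

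**The case against.** A reader might infer that new blood-pressure elevation cannot be shown at all and that the endpoint goes unanswered. The documents do not support that:

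- SAP 5.7.1 defines treatment-emergent events as those that occur or worsen after the first dose. It tabulates them by preferred term, gives exposure-adjusted rates, and counts patients with abnormal vital signs reported as such events. The Study 007 signal was itself made of adverse event reports.
- SAP 6.1 maps Baseline as an analysis visit, so the by-visit tables can include it.
- SAP 5.1 lists every CRF module by patient.

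These routes give partial cover. Adverse event reporting has the threshold described above. By-visit levels are unpaired, in a set of patients that changes with early termination and transfer to commercial drug. A listing is not an analysis.

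It can also be argued that nothing was dropped. Silence is not a conflict, SAP 7 removes only the tests, and the protocol's plan is qualified by where appropriate. That is a possible reading. It makes the point an ambiguity rather than a proven deletion, and a sentence in SAP 5.8.1 would settle it.

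Three further inferences should be resisted:

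- **That the planned count is inflated by repeated measurement.** This holds only if it means at any visit, which the SAP does not say.
- **That the adult classes need a new definition of Normal.** A systolic value below 90 or a diastolic value below 60, with the other value normal, does fall in no class. This does not alter the number hypertensive, and widening Normal would hide low pressure.
- **That percentiles cannot be computed for non-ambulatory boys.** Protocol 7.5 says "ulna length and arm span will be used as a surrogate measure for height" and refers to the Study Manual, which is not among the documents.

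**Conclusion.** The point stands as a gap in specification. SAP 5.8.1 assigns no change-from-baseline analysis to a named secondary safety endpoint, SAP 7 does not declare the omission, and the hypertension count cannot distinguish new from pre-existing elevation. No sample size, power or error rate depends on it. The 0-to-66 range is an illustration that rests on the assumed 30%; the ambiguity itself does not depend on that figure.

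The Study 007 counts justify a proper table but do not establish a drug effect. The comparison with placebo is imprecise, and the higher dose had no reports.

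The remedy also has a limit. The 020e baseline follows the 48-week parent study, so for ataluren/ataluren patients it is an on-drug value. Only placebo/ataluren patients can show onset after starting ataluren, and they have no concurrent control. This should be corrected, but it does not threaten the study's main conclusions.

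**What to change.** In SAP 5.8.1:

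1. Add change from baseline by visit for systolic pressure, diastolic pressure, pulse and weight, using the formula already in SAP 6.3.
2. Replace the single hypertension count by a shift table from baseline category to the category at each visit and to the worst on-treatment category. Add the number of patients not hypertensive at baseline who meet the criterion at two or more consecutive on-treatment visits.
3. Show both by parent-study arm (ataluren/ataluren, placebo/ataluren), a grouping SAP 5.8.4 already uses, and state that the baseline is on-drug for the first group.

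If the sponsor prefers not to report the changes, SAP 7 should say so and give the reason.

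The cost is SAP wording and a few tables. All the data are already collected.

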### 5.8.2. ECGs

Number (%) of subjects experiencing a normal/abnormal ECG assessment will be tabulated by visit for overall subjects.

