Most patients with dystrophinopathy are characterized as having DMD; these patients experience onset of symptoms during early childhood [Ciafaloni 2009]. A small subset (~10%) of boys is classified as having BMD, a phenotypically milder form of dystrophinopathy that is associated with later manifestation of symptoms [Emery 1991]. DMD usually first manifests in boys ~3 to 7 years of age when they are noted to develop lordosis, a waddling gait, and the Gowers' sign (a characteristically abnormal method of rising from a supine to a standing position) [Brooke 1989, McDonald 1995, Boland 1996, Worton 2001]. Inexorable progressive weakness is seen, particularly in the proximal musculature. Ambulation becomes increasingly abnormal. By the age of 8 years, most boys have difficulty rising from the floor and ascending stairs and they often fall while walking. Boys with the disease spend less time walking and walk more slowly than healthy boys [McDonald 2005a] and are significantly less active than normal boys of similar age [McDonald 2002, McDonald 2005b]. By 10 to 14 years of age, most are wheelchair-bound. In ambulatory DMD boys, the most frequent cardiac abnormality is sinus tachycardia and heart rate variability, occurring from childhood and persisting throughout life [Finsterer 2003, Gulati 2005]. Pulmonary function is usually normal before 10 years of age and is well

maintained into adolescence in boys receiving corticosteroids [Mendell 1989, Griggs 1991, Phillips 2001, Tangsrud 2001, Biggar 2001, Biggar 2006]. Later in adolescence, cardiac and diaphragmatic muscles become progressively weaker and patients require treatment for cardiac insufficiency and ventilatory support. Patients usually die of cardiac or pulmonary failure by 15 to 22 years of age [Brooke 1989, McDonald 1995, Simonds 1998, Worton 2001, Eagle 2002].

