8. ADVERSE EVENT ASSESSMENTS

8.1. Adverse Event Definitions

8.1.1. Adverse Events

An adverse event is any untoward medical occurrence associated with the use of a drug (investigational medicinal product) in humans, whether or not it is considered related to the drug. An adverse event can therefore be any unfavorable and unintended sign (including an abnormal laboratory finding), symptom, or disease in a study patient who is administered study drug in this study.

For this protocol, untoward medical occurrences that should be reported as adverse events include the following:

- All adverse events that are suspected to be due to study drug.
- Overdose (administration of a study drug dose >4 times the highest intended total daily dose level for this protocol [>160 mg/kg/day]) of study drug.
- All reactions from medication misuse, abuse, withdrawal, sensitivity, or toxicity.

- All reactions that result from medication errors or uses of the study drug outside what is described in the protocol.
- Apparently unrelated illnesses, including the worsening of a preexisting illness.
- Injury or accidents. Note that if a medical condition is known to have caused the injury or accident (a fall secondary to dizziness), the medical condition (dizziness) and the accident (fall) should be reported as 2 separate adverse events. The outcome of the accident (hip fracture secondary to the fall) should be recorded in source documents.
- Abnormalities in physiological testing or physical examination findings that require clinical intervention or further investigation (beyond ordering a repeat [confirmatory] test).
- Laboratory or ECG abnormalities that require clinical intervention or further investigation (beyond ordering a repeat [confirmatory] test) unless they are associated with an already reported clinical event. Laboratory abnormalities associated with a clinical event (eg, elevated liver enzymes in a patient with jaundice) should be captured in the source documents. Laboratory abnormalities not requiring clinical intervention or further investigation will be captured as part of overall laboratory monitoring, and should not be reported as adverse events.

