ECG data will be listed and summarized by treatment period and overall, and will be checked for changes from baseline over time.

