Listings of death, serious AEs, AEs leading to discontinuation from treatment, and hepatic and renal AEs leading to special diagnostic evaluations will be provided.

The drug exposure adjusted TEAE incidence rate will be summarized by SOC and PT, where the incidence rate of the TEAE per 100 patient-year = (number of events/number of patient-years) \*100. The number of patient-years is defined as the sum of the number of days on study drug of all patients divided by 336. That is, a year is defined as 48 weeks.

In addition, the number of subjects with clinical laboratory abnormalities, abnormal vital signs, and abnormal electrocardiogram reported as TEAE will be summarized.

Non-serious TEAE will be displayed by SOC and PT. The common non-serious TEAE (subject frequency of  $\geq 5\%$ ) will also be displayed by SOC and PT.

Numbers of occurrence of serious TEAE and the numbers of occurrence of non-serious TEAE will be summarized by SOC and PT, separately.

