### 5.8.11. Physical Examination

Since abnormal findings in physical examination need to be reported in AE and vital signs, a data listing of physical examination will be provided.

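### No planned summary table counts new ECG or physical examination abnormalities that were not reported as adverse events, because the ECG table shows only net change and physical examination is only listed

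*SAP*

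**What the plan says.** **ECG.** Protocol 10.4.3, under the primary safety variables: "ECG data will be listed and summarized by treatment period and overall, and will be checked for changes from baseline over time". SAP 5.8.2 plans: "Number (%) of subjects experiencing a normal/abnormal ECG assessment will be tabulated by visit for overall subjects". It specifies no shift table, no clinical-significance category and no change from baseline. SAP 5.7.1 adds one further ECG output: "the number of subjects with clinical laboratory abnormalities, abnormal vital signs, and abnormal electrocardiogram reported as TEAE will be summarized".

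**Physical examination.** Protocol 10.4.3 says that "physical examination data will be listed and summarized by visit and overall". SAP 5.8.11 reads: "Since abnormal findings in physical examination need to be reported in AE and vital signs, a data listing of physical examination will be provided".

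**What becomes an adverse event.** The list in Protocol 8.1.1 includes "Abnormalities in physiological testing or physical examination findings that require clinical intervention or further investigation (beyond ordering a repeat [confirmatory] test" and, in a separate item, "Laboratory or ECG abnormalities that require clinical intervention or further investigation". The ECG item leaves out abnormalities that belong to a clinical event already reported.

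**Other relevant provisions.** SAP 5.1 promises a by-patient listing of each CRF module, ordered by subject and visit. SAP 5.7.2 and 5.8.10 plan shift tables for laboratory data and renal ultrasound. SAP 3.3 keeps change from baseline in other safety parameters as an endpoint. SAP 7 names two changes from the protocol: removal of the supportive 6MWT analyses and removal of all paired t-tests. SAP 1 gives the SAP precedence over the protocol.

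**The concern.** Long-term safety is the primary objective and there is no concurrent control arm, so each boy's change from his own baseline is the most direct evidence available. The percentage abnormal at each visit does not use that pairing. Abnormalities that appear and abnormalities that resolve cancel, and the denominator changes as boys leave.

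The exclusion criteria do not bar every abnormal ECG. Exclusion 3 applies only when the investigator judges the finding a problem, so pre-existing abnormalities can sit in the same percentage as new ones. Protocol 2.1 gives a disease-related reason to expect some, saying that in ambulatory boys "the most frequent cardiac abnormality is sinus tachycardia and heart rate variability, occurring from childhood and persisting throughout life".

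For physical examination, the SAP's reason for dropping the summary is that abnormal findings reach other tables. If some do not, they appear only in a listing. The safety report could then not state how many boys developed a new abnormality on either measure unless it was reported as an adverse event.

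**Working it through.** The documents state no ECG or physical examination figure, so there is nothing to reproduce. The check has three parts.

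**1. What the ECG table can determine.** Take n boys with an ECG at both baseline and a visit. Let a1 be the number abnormal at baseline, a2 the number abnormal at the visit, x the number going from normal to abnormal, and y the number going from abnormal to normal. Then a2 = a1 + x − y, with 0 ≤ y ≤ a1 and 0 ≤ x ≤ n − a1. The table gives a1 and a2 only, so

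max(0, a2 − a1) ≤ x ≤ min(a2, n − a1).

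The figure n = 220 is the approximate upper bound in SAP 3.4. The smaller n and all abnormality rates are assumptions, and pairing is taken as complete.

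| n | Abnormal at baseline | Abnormal at visit | Newly abnormal boys compatible with the table |
|---|---|---|---|
| 220 | 22 (10%) | 22 (10%) | 0 to 22 |
| 220 | 44 (20%) | 44 (20%) | 0 to 44 |
| 220 | 66 (30%) | 66 (30%) | 0 to 66 |
| 220 | 44 (20%) | 55 (25%) | 11 to 55 |
| 220 | 66 (30%) | 55 (25%) | 0 to 55 |
| 100 | 20 (20%) | 20 (20%) | 0 to 20 |

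A shift table reports x directly.

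**2. Drop-out, on assumed figures.** Start with 200 boys, 100 of them abnormal. Suppose 20 normal boys become abnormal and 10 abnormal boys revert.
- With nobody leaving: (100 + 20 − 10)/200 = 110/200 = 55%, against 50% at baseline.
- With 25 leavers, all from the 90 boys abnormal throughout: (110 − 25)/(200 − 25) = 85/175 = 48.6%.
- With 25 leavers unrelated to ECG status: about 55%.

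In the first two cases new abnormality among boys normal at baseline is 20/100 = 20%, and in the third it is about 20% of those still followed. The by-visit percentage falls on either side of 50% depending on who leaves.

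**3. The physical examination premise against the protocol.** SAP 5.8.11 treats abnormal findings as reportable under adverse events or vital signs. Protocol 8.1.1 lists those needing intervention or work-up beyond a repeat test. Protocol 7.5 has the examination cover systems such as thyroid, skin, spine and lymph nodes, which no vital sign captures. A new finding there that needs no action is not named in the adverse event list and has no vital-sign entry. The premise therefore does not cover all abnormal findings.

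Dropping the paired t-tests, which SAP 7 does declare, accounts for the testing that Protocol 10.4.3 attaches to these data. It does not account for dropping the by-visit physical examination summary or the ECG check for change from baseline.

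**The case against.** The strongest reply is that little is hidden. ECG findings go on the CRF (Protocol 7.10), and listings by subject and visit let a reader pair baseline with later results. Abnormal ECGs reported as treatment-emergent events are counted, and by definition those events occur or worsen after first dose in this study. Pulse rate is summarised by visit in SAP 5.8.1. Boys who stop early are to have the Week 144 procedures, including ECG and physical examination, and events leading to discontinuation are tabulated. All of this stands. A reader might infer that neither measure can show a new abnormality; the listings and the event count show that this is not so.

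Other parts of the reply also stand:
- Protocol 8.1.1 does not flatly contradict the SAP. Its general definition of an adverse event is broad, its list is introduced as inclusive, and only laboratory abnormalities below the threshold are expressly kept out. The SAP's premise is incomplete; the text does not show it to be simply false.
- Protocol 2.1 names the most frequent cardiac abnormality but gives no prevalence. It does not establish that many boys enter with an abnormal ECG.
- Protocol 10.4.3 asks for a check on change from baseline without prescribing a shift table. A by-visit table that includes baseline meets that in part, at group level.
- The documents do not show that the CRF records normal/abnormal status by body system.

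What the reply does not answer is that reading listings for up to about 220 boys is no substitute for a count. The event count is also limited by the reporting threshold, and it omits ECG abnormalities folded into an already reported clinical event.

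**Conclusion.** The point holds in this form: no planned summary table counts new ECG or physical examination abnormalities that were not reported as adverse events. The protocol's ECG check against baseline and its by-visit physical examination summary have been reduced, and SAP 7 records neither.

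The size of the ECG gap depends on rates the documents do not give. On assumed rates of 10% to 30% abnormal at both times among 220 paired boys, the table leaves the number of new abnormalities undetermined between 0 and 22 to 66.

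Two further readings are tempting and are not supported. The first is that drop-out would make the ECG table look like improvement. That needs the leavers to be mainly boys with abnormal ECGs, and with unrelated drop-out the assumed example shows worsening. The second is that a shift from baseline would identify abnormalities new on ataluren. SAP 6.2 sets baseline at first dose in this study, and SAP 5.8.4 recognises an ataluren/ataluren group already treated in Study 020. For those boys the shift shows only what is new during the extension.

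The consequence is modest. The study is descriptive, the primary endpoint is adverse events and laboratory abnormalities, and findings that need action should still reach the adverse event tables. The change is worth making because it restores a check the protocol asked for with a method the SAP already uses elsewhere.

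**What to change.** - **SAP 5.8.2:** add an ECG shift table from the 020e baseline to each ECG visit and to the worst post-baseline ECG. Use normal/abnormal, with clinical significance if the CRF holds it. Report newly abnormal boys over those who were normal at baseline and had a post-baseline ECG. Split by prior treatment (ataluren/ataluren, placebo/ataluren) and describe the result as new during the extension. State whether unscheduled and six-week post-treatment ECGs count towards the worst value.
- **SAP 5.8.11:** correct the premise so that it matches Protocol 8.1.1, and restore the by-visit physical examination summary. If the CRF records normal/abnormal status by body system, make it a shift table, since a by-visit summary alone again shows only net change.
- **SAP 7:** list and justify any reduction from Protocol 10.4.3 that remains.
- Keep the listings and the count of abnormal ECGs reported as treatment-emergent events.

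The cost is SAP wording and one or two further tables. The ECG table uses data already collected; the physical examination shift table depends on how the CRF was built. The downside is a slightly longer safety output.
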